patient's antibiotic treatment plus seven days post-antibiotic treatment.

**Group 2:** This group will receive 30 oral FMT capsules one time 48-72 hours following completion of antibiotic treatment.

**Oral FMT capsules:** Capsules contain fecal microbiota sourced from healthy donors and screened for pathogens.

**Control:** The control is an oral placebo capsule identical to the FMT capsules given to the intervention groups and will be provided by OpenBiome. The placebo capsule consists of glycerol and saline and will be administered daily as five capsules per day during the duration of antibiotic treatment plus an additional seven days post-antibiotic treatment (group 3). Patients will be fasting (clear liquids allowed) for at least 2 hours prior to administration and at a minimum of 1-hr post-administration (Appendix 17.1)

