### **8.3. Exclusion Criteria**

1. Admitted to an intensive care unit (ICU).
2. Females who are pregnant, lactating, or planning to become pregnant during the study. Female patients of childbearing potential will take a pregnancy test at the intervention visit and will be excluded if pregnant.
3. Inability (e.g. dysphagia) to or unwilling to swallow capsules.
4. Known or suspected toxic megacolon and/or known small bowel ileus.
5. Bowel obstruction or other gut motility issues occurring in the last two weeks that are unresolved as noted by the patient or in the EMR.
6. Major gastrointestinal surgery (e.g. significant bowel resection) within 3 months before enrollment not including appendectomy or cholecystectomy.
7. History of bariatric or colectomy surgery.

8. Concurrent intensive induction chemotherapy, radiation therapy, or biologic treatment for an active malignancy. Patients on maintenance chemotherapy may be enrolled after consultation with the medical monitor.
9. Expected life expectancy <6 months.
10. Patients with severe anaphylactic or anaphylactoid food allergy.
11. Solid organ transplant recipients ≤90 days post-transplant or on active treatment for rejection.
12. Neutropenia ( $\leq 500$  neutrophils/mL) or other severe immunosuppression. Anti-TNF will be permitted. Patients on monoclonal antibodies to B and T cells, glucocorticoids, antimetabolites (azathioprine, 6-mercaptopurine, methotrexate), calcineurin inhibitors (tacrolimus, cyclosporine), and mycophenolate mofetil may only be enrolled after consultation with the medical monitor.\*
13. At risk of CMV/EBV associated disease, negative IgG testing for cytomegalovirus (CMV) or Epstein Barr Virus (EBV).
14. Any other gastrointestinal illness including diarrhea.
15. On oral vancomycin or metronidazole.
16. Having been taking the currently prescribed antibiotic for over 72 hours.
17. On an antibiotic treatment anticipated to exceed 19 days.
18. Having received an FMT by any route in the 90 days prior to enrollment.
19. Any condition that would jeopardize the safety or rights of the patient, would make it unlikely for the patient to complete the study, or would confound the results of the study.

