## **8.4. Subject Screening and Retention**

### ***8.4.1. Subject Identification***

Potential subjects will be identified by the study team who has access to a list of patients admitted to UWHC for infectious diseases that is updated daily. The medical monitor will screen these patients' EMR to determine eligibility. Once potential subjects meeting the eligibility criteria are identified, the treatment team's physician or nurse will ask the patient if he/she is interested in hearing about the study and if so, will introduce the research team. The patient will be invited to hear about the study and, if interested and meeting all eligibility criteria, participate in the study. As patients with community acquired pneumonia (CAP) and urinary tract infections (UTIs) are likely to be on shorter antibiotic courses, initial recruitment will focus on these patients. We, however, do not plan to limit to just CAP and UTI patients and will consider patients admitted to other non-ICU acute care units or outpatients with anticipated short courses (2 weeks or fewer) of antibiotic treatment.

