#### **8.4.2.2. *Retention***

Stool samples will be taken from all subjects at baseline and every 3 days  $\pm$  1 day regardless of treatment group while the patient is hospitalized. If/when a patient is discharged from the hospital, the patient will continue to provide stool samples every three days during FMT and once weekly for 4 weeks following FMT. We will call or email the patient weekly until they have completed FMT and once weekly during follow-up to remind him/her to mail us a stool sample and discuss the patient diary. If the patient is receiving either the daily FMT or placebo, we will also remind him/her to be taking his/her capsules as well as ask him/her to count how many pills he/she currently has left for us. If a patient in the one-time FMT group is discharged prior to the FMT consumption time point (48-72 hours post antibiotic treatment completion), he/she will be asked to return to the ID clinic or CRU to receive his/her FMT capsules. Inpatients in the daily and placebo groups will have each dose of 5 capsules observed by a nurse/physician during admission and will be discharged with a cooler containing their FMT capsules and instructed on use. Outpatients in the daily and placebo groups will be asked to come to the ID clinic or CRU to have their first dose observed by a nurse or physician and be given the remaining FMT doses to take home. After discharge, all patients will receive a study brochure tailored to their study arm describing all post-discharge study procedures.

While we will target patients who are on antibiotic doses with a duration of less than 14 days, if a patient's antibiotic regimen exceeds 14 days will be handled in the following manner:

Group 1: Patients will be given the 30 capsule dose of FMT on day 16 or 17 (day 14 + 48 to 72 hours) of antibiotic treatment unless they meet one of the criteria for halting a patient's participation in the study (13.5.2). Participants who are not withdrawn from the study will continue follow-up the same as other patients.

Groups 2 and 3: At 14 days of antibiotics, we will discontinue the daily FMT treatments and patients will move to the weekly follow-up phase of the study unless they meet one of the criteria in section 13.5.2 in which case they will be withdrawn from the study.

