## **9.8. Modification of Study Intervention/Investigational Product for a Participant**

If the participant is unable to complete the full dose of DE or placebo in one sitting the actual dose ingested will be recorded. Further study product administration, including the remainder of the incomplete dose and scheduled upcoming doses as applicable will be at the discretion of the treating physician. The remaining capsules scheduled to be administered may be offered to the participant on the same day they were scheduled. Intention-to-treat analysis will be utilized according to best practices in clinical trials.

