### *Group 1 (daily FMT) and Group 3 (daily placebo): Will occur in a clinical setting for inpatients.*

Capsules will be delivered to the patients every day by a blinded member of the treatment team during the time they are admitted. If the patient is discharged or an outpatient, he/she will be provided with enough capsules to complete the study and will be asked to consume 5 capsules per day while on antibiotics as well as for 7 days post-antibiotic treatment completion. Outpatients and patients discharged during the follow-up period will be called or emailed (depending on patient preference) weekly to remind them to take their capsules as well as to send in their stool samples every three days (+/- 1 day). The researcher calling the subject will also ask the subject to count the number of pills he or she has remaining (recorded in the patient diary) and ask about any adverse events or changes to medications and diet. Study staff do not need to collect a blood sample to monitor for neutropenia. If the subject has any capsules remaining after completion of study intervention (e.g. missed doses, shortened antibiotic course after study intervention has been dispensed), the subject will be asked to return the remaining capsules to the Infectious Disease Research lab.

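### Exclusion 17 admits planned antibiotic courses of 15 to 19 days, for which section 8.4.2.2 cuts short the daily regimen and mistimes the single dose

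*Combined protocol and SAP*

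**What the plan says.** Section 8.3, item 17, sets the only numerical limit on planned course length: the patient is excluded if "On an antibiotic treatment anticipated to exceed 19 days".

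The regular regimens are tied to the end of antibiotics. For the single-dose arm, section 7.1 states: "This group will receive 30 oral FMT capsules one time 48-72 hours following completion of antibiotic treatment". For the daily FMT and daily placebo arms, section 11.2 says discharged patients and outpatients are "asked to consume 5 capsules per day while on antibiotics as well as for 7 days post-antibiotic treatment completion".

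Section 8.4.2.2 then says how a patient whose "antibiotic regimen exceeds 14 days will be handled in the following manner". The 30-capsule dose is given "on day 16 or 17 (day 14 + 48 to 72 hours) of antibiotic treatment". For daily capsules, at 14 days of antibiotics "we will discontinue the daily FMT treatments and patients will move to the weekly follow-up phase of the study".

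Recruitment text points to shorter courses. Section 8.4.2.2 says the team targets courses under 14 days, and section 8.4.1 mentions "outpatients with anticipated short courses (2 weeks or fewer) of antibiotic treatment". Neither statement is an eligibility criterion.

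The group numbers in 8.4.2.2 do not match those in 7.1. That is a separate matter. Here the rule is read by regimen (daily or single dose), whatever the group number.

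**The concern.** Two current sections use different limits for the same quantity. The eligibility limit is 19 days and the limit for delivering the regular regimen is 14. Patients in between are identifiable before randomization, because item 17 itself asks for the anticipated duration.

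The objective in the Study Summary compares FMT given during antibiotics, FMT given just after them, and placebo. In a 15 to 19 day patient the arm meant to be dosed afterwards can be dosed while antibiotics continue, and the daily FMT arm loses its post-antibiotic week. Both changes blur the contrast between the two FMT strategies.

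Primary-outcome sampling moves as well. The weekly stool phase starts when the intervention ends, so for capped daily patients it starts while they are still on antibiotics.

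The arms are small. Sections 8.1 and 12.2 plan 10 enrolled and 8 analyzable patients per group, so one such patient is 1/10 = 10% to 1/8 = 12.5% of an arm.

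**Working it through.** **Inputs.** L is the course length in days, with antibiotic day 1 as the first day. Eligible lengths above 14 are L = 15 to 19 (8.3, item 17). The regular daily regimen runs to day L + 7 (7.1, 11.2). The regular single dose is 48 to 72 hours after antibiotics end, that is +2 to +3 days (7.1). For L > 14, daily dosing ends on day 14 and the single dose is on day 16 or 17 (8.4.2.2).

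**Assumptions.** The course runs as planned. The first daily capsule is taken on day s = 1 to 4, because enrollment must fall within 72 hours of starting the antibiotic (8.2, item 6).

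**The plan's own figure.** 14 + 2 = 16 and 14 + 3 = 17, so day 16 or 17 reproduces. The rule treats every longer course as if it had ended on day 14.

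| L | Regular last daily dose (L + 7) | Last daily dose under 8.4.2.2 | Dosing days lost | Antibiotic days without capsules | Single dose relative to last antibiotic day |
|---|---|---|---|---|---|
| 14 | 21 | 21 | 0 | 0 | +2 or +3 |
| 15 | 22 | 14 | 8 | 1 | +1 or +2 |
| 16 | 23 | 14 | 9 | 2 | 0 or +1 |
| 17 | 24 | 14 | 10 | 3 | −1 or 0 |
| 18 | 25 | 14 | 11 | 4 | −2 or −1 |
| 19 | 26 | 14 | 12 | 5 | −3 or −2 |

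**Daily arms.**
- Planned dosing days = L + 7 − s + 1: 22 to 26 for s = 1, and 19 to 23 for s = 4.
- Given = 14 − s + 1: 14 for s = 1, and 11 for s = 4.
- Lost = (L + 7) − 14 = L − 7: 8 to 12 days, always including all 7 post-antibiotic days.
- Share lost: smallest 8/22 = 36.4% (L = 15, s = 1), largest 12/23 = 52.2% (L = 19, s = 4).
- Capsules lost: 5 × 8 = 40 to 5 × 12 = 60, out of 5 × 19 = 95 to 5 × 26 = 130 planned.
- There is a step at the boundary. A 14-day course gives 21 dosing days (s = 1) or 18 (s = 4), and a 15-day course gives 14 or 11. One more antibiotic day means 7 fewer doses.

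**Single-dose arm.** The assigned timing is +2 to +3. Only L = 15 with dosing on day 17 reaches +2. Every 16 to 19 day course misses the window. For L = 17 to 19 the dose always falls on or before the last antibiotic day, and for L = 18 and 19 always before it.

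**Stool sampling, daily arms.** Four weekly samples after the intervention take the regular schedule to day L + 7 + 28 = L + 35, which is 35 days after antibiotics end. Under the cap it ends on day 14 + 28 = 42, which is 42 − L = 27 (L = 15) to 23 (L = 19) days after antibiotics end. That is 8 to 12 days less post-antibiotic sampling.

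**Does another provision close the gap?** No other criterion in 8.2 or 8.3 sets a 14-day limit. Exclusion 19 is a discretionary catch-all, and the wording in 8.4.1 and 8.4.2.2 about shorter courses describes whom the team seeks.

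**The case against.** The strongest reply is that the plan provides for these patients. Section 8.4.2.2 gives a stop day, a dosing day and continued follow-up, and eligibility somewhat wider than the target is defensible in a pilot whose size (12.1) depends on how many patients are available. That holds for courses that overrun unexpectedly. It does not explain why patients expected from the outset to need the exception should be randomized.

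Second, few such patients may be enrolled. Recruitment prefers pneumonia and urinary tract infections, which section 8.4.1 expects to have shorter courses, and exclusion 19 could be invoked. This stands as a limit on size: the frequency is unknown and could be near zero. It does not remove the gap, and if such patients are rare, closing it costs little.

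Third, the primary objective in section 6 and aim 1 in 5.2 compare FMT with placebo, and the daily FMT and daily placebo arms are capped alike. This also stands. For that contrast the effect is less FMT received, not an imbalance in schedule. The contrast between the two FMT strategies is still affected.

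Fourth, it is not settled how these patients would be analysed. Section 9.8 says "Intention-to-treat analysis will be utilized according to best practices in clinical trials", but in the context of incomplete doses, while 12.2 refers to patients who complete treatment. Whether a capped patient counts as a completer is left open. If kept, such patients blur the comparison; if dropped, they reduce arms of 10.

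**Conclusion.** The concern holds on the current text. Item 17 admits planned 15 to 19 day courses for which 8.4.2.2 replaces the assigned regimen. The only deliverable case is a 15-day course in the single-dose arm dosed on day 17.

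Per affected patient the departure is large: roughly a third to a half of daily dosing is lost, or a single dose meant to follow antibiotics comes too early, often while they continue. Across the trial the size cannot be stated, because the documents give no distribution of course lengths. The result assumes that courses run as planned, that daily dosing starts within the 72-hour enrollment window, and that 8.4.2.2 is read by regimen. This is a correction that should be made; it does not undermine the trial.

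**What to change.** In section 8.3, item 17, change the limit from 19 to 14 days, and state that it applies to the qualifying new antibiotic course, not to the long-term prophylaxis that section 9.9 allows. Without that clause the lower limit could be read as barring those patients. In 8.4.2.2, state that the 14-day rule is for courses extended after enrollment.

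Every planned course then fits both regimens. At the new maximum of 14 days, daily dosing runs to day 14 + 7 = 21 and the single dose falls on day 16 or 17, which is 48 to 72 hours after antibiotics end.

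The cost is one number and two short clauses, plus the loss of patients with planned 15 to 19 day courses. Their number is unknown, and recruitment is a feasibility outcome (7.2.2), but the protocol says it does not target them. If the investigators want to keep them, the alternative is to raise the cap in 8.4.2.2 to 19 days and deliver the full regimen. That means up to 26 dosing days (130 capsules) per daily patient, against 21 (105) for a 14-day course. The documents give no reason for the 14-day cap, so whether it can be raised is for the investigators to judge.

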## **8.4. Subject Screening and Retention**

### ***8.4.1. Subject Identification***

Potential subjects will be identified by the study team who has access to a list of patients admitted to UWHC for infectious diseases that is updated daily. The medical monitor will screen these patients' EMR to determine eligibility. Once potential subjects meeting the eligibility criteria are identified, the treatment team's physician or nurse will ask the patient if he/she is interested in hearing about the study and if so, will introduce the research team. The patient will be invited to hear about the study and, if interested and meeting all eligibility criteria, participate in the study. As patients with community acquired pneumonia (CAP) and urinary tract infections (UTIs) are likely to be on shorter antibiotic courses, initial recruitment will focus on these patients. We, however, do not plan to limit to just CAP and UTI patients and will consider patients admitted to other non-ICU acute care units or outpatients with anticipated short courses (2 weeks or fewer) of antibiotic treatment.

### ***8.4.2. Recruitment and Retention***

#### ***8.4.2.1. Recruitment***

Adult inpatients that are on infectious control list secondary to a recent (90 day) CDI diagnosis and potentially meet the inclusion criteria will be invited to join the study. If patients have been discharged before recruitment, we will utilize the 'mailed letter option' signed by the study PI with clear study descriptions to reach them and schedule a day/time for a phone screening. We will follow-up this

letter with up to three phone calls. If the subject does not respond to the letter or any calls, they will be considered not interested in the study.

If the study team identifies an outpatient through screening that has not previously been contacted and appears to be potentially eligible a study team member will cold call them (using specific telephone script) to assess their interest in the study without mailing a letter first due to the 72-hour enrollment window. If they are interested and meet inclusion criteria they will be invited to a clinic visit for further screening and possible study enrollment.

Potentially eligible patients will also be recruited from ambulatory settings. Clinic providers will be given information on the study and eligibility criteria in order to assess the patient's interest in the study. Interested patients will be contacted by a study team member to further discuss the study and meet for the enrollment visit if indicated. Inpatients who have a diagnosis of CDI within the past 90 days will be approached by the study team to introduce the study and provide contact information for the study should the patients be prescribed antibiotics not targeting CDI.

The mailed letter option may also be utilized for those with known CDI within the past 90 days to alert them to the study with contact information should they be prescribed antibiotics and be interested in joining the study. One method research teams will use to identify potentially eligible patients from ambulatory settings is through viewing schedules of clinics that have a high percentage of potential subjects. These include Infectious Disease, Transplant and Primary Care clinics, and may expand as other focus areas are identified. Patients from these clinic lists will be prescreened for eligibility and approached as previously described. This prescreening process will help ensure only patients who are likely to meet eligibility criteria are approached.

If available, software (ex: Clinithink) may be used as screening aids provided they meet standards for data confidentiality as outlined in the protocol and IRB approval is obtained.

#### **8.4.2.2. *Retention***

Stool samples will be taken from all subjects at baseline and every 3 days  $\pm$  1 day regardless of treatment group while the patient is hospitalized. If/when a patient is discharged from the hospital, the patient will continue to provide stool samples every three days during FMT and once weekly for 4 weeks following FMT. We will call or email the patient weekly until they have completed FMT and once weekly during follow-up to remind him/her to mail us a stool sample and discuss the patient diary. If the patient is receiving either the daily FMT or placebo, we will also remind him/her to be taking his/her capsules as well as ask him/her to count how many pills he/she currently has left for us. If a patient in the one-time FMT group is discharged prior to the FMT consumption time point (48-72 hours post antibiotic treatment completion), he/she will be asked to return to the ID clinic or CRU to receive his/her FMT capsules. Inpatients in the daily and placebo groups will have each dose of 5 capsules observed by a nurse/physician during admission and will be discharged with a cooler containing their FMT capsules and instructed on use. Outpatients in the daily and placebo groups will be asked to come to the ID clinic or CRU to have their first dose observed by a nurse or physician and be given the remaining FMT doses to take home. After discharge, all patients will receive a study brochure tailored to their study arm describing all post-discharge study procedures.

While we will target patients who are on antibiotic doses with a duration of less than 14 days, if a patient's antibiotic regimen exceeds 14 days will be handled in the following manner:

Group 1: Patients will be given the 30 capsule dose of FMT on day 16 or 17 (day 14 + 48 to 72 hours) of antibiotic treatment unless they meet one of the criteria for halting a patient's participation in the study (13.5.2). Participants who are not withdrawn from the study will continue follow-up the same as other patients.

Groups 2 and 3: At 14 days of antibiotics, we will discontinue the daily FMT treatments and patients will move to the weekly follow-up phase of the study unless they meet one of the criteria in section 13.5.2 in which case they will be withdrawn from the study.

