## 2. STUDY SUMMARY

Title	A phase II randomized, double-blind placebo-controlled trial to determine if fecal microbiota transplantation is efficacious for hospitalized patients with C. difficile infection history during antibiotic treatment
Short Title and Precis	The GRAFT study
Protocol Number	2017-0789
ClinicalTrials.gov number	NCT03621657
Funding Sponsor	Agency for Healthcare Research and Quality (AHRQ) [name] [contact]
Study Product	OpenBiome fecal microbiota preparation capsule [FMT Capsule DE]
Phase	Phase II study
Methodology	Randomized, double-blind, placebo-controlled trial
Study Duration	1 year
Study Center(s)	Single-center, University of Wisconsin Hospitals and Clinics
Objectives	The primary objective of this study is to compare the gut microbiota and clinical outcomes of oral FMT during antibiotic treatment, immediately following antibiotic treatment, and placebo. The second objective is to assess the safety and feasibility of daily oral Fecal Microbiome Transplant (FMT) as a treatment option.
Number of Subjects	30 (1:1:1 randomization), 10 subjects per group
Diagnosis	Changes in the gut microbiota and C. difficile infection (CDI)
Main Inclusion Criteria	Receiving antibiotics for reasons other than CDI following a recent CDI episode (within last 90 days)
Main Exclusion Criteria	Bowel obstruction or gut motility issues, severely immunocompromised, or admitted to the ICU.
Study Product, Dose, Route, Regimen	FMT will be delivered through oral capsules prepared by OpenBiome. It will be administered in one of two ways depending on the arm of the trial. 1) A low dose of 5 capsules per day during antibiotic treatment and for seven days following conclusion of antibiotics. 2) A single dose of 30 capsules (22.5g) of oral FMT will be given 48-72 hours after antibiotic treatment conclusion.
FDA status of product	Encapsulated fecal microbiota preparation (FMT Capsule DE). Please refer to Finch Therapeutics BBMF # 17194.
	Sourced from human-derived microbes. Please refer to OpenBiome BBMF # 15543, Section F.
	IND: 18262

**Duration of administration** Group 1: 5 capsules of oral FMT per day undergoing antibiotic treatment and for 7 days following conclusion of antibiotic treatment.

Group 2: 30 capsules taken 48-72 hours following conclusion of antibiotic treatment

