### **7. STUDY DESIGN AND ENDPOINTS**

#### **7.1. General Design**

This is a phase II, double-blind, randomized, placebo controlled trial assessing the effects of either daily (group 1) or one-time (group 2) oral FMT on the composition and function of the gut microbiome compared to placebo (group 3) in a population of patients with a history of CDI currently on antibiotics for a reason other than current CDI. Participants will be 18 years of age or older, have 72 hours or less of an antibiotic and meet all inclusion criteria while having no exclusion criteria prior to randomization. Patients will be randomized at a 1:1:1 ratio using permuted blocks (block size=10). Randomization will be double-blinded. Each subject (n=30) will be followed for 6 months. Stool samples will be taken at baseline and every 3 days  $\pm$  1 day from all subjects regardless of treatment group while the patient is hospitalized. If/when a patient is discharged from the hospital, the patient will continue to provide stool samples every three days during FMT. Following completion of the FMT intervention, the patient will provide stool samples once weekly for the 1 month follow-up period. All patients will be asked to complete a patient diary to report diarrhea history.

Up to one gram of stool will be sent to Finch therapeutics for additional 16s rRNA sequencing.

**Intervention:** There are 2 intervention groups for this study. Both groups will receive oral FMT capsules from OpenBiome for the prevention of CDI during antibiotic treatment. All patients will fast (clear liquids only) for a minimum of 2 hours prior to administration and 1-hour post-administration for the daily groups and be fasting for 8 hours prior and 1 hour post FMT consumption for the single dose group. The capsules will be administered in the patient's room while admitted or in the ID clinic or CRU if the patient is an outpatient and the first dose will occur under direct observation. Patients admitted to the hospital as well as all patients in the single dose group will be observed for 30 minutes post-administration to ensure the capsules are safely consumed. Hospitalized patients need to be observed 30-minutes post-administration following only the first dose. As mentioned above, the oral FMT capsules will be administered in two ways:

**Group 1:** This group will receive daily oral FMT capsules. Five capsules will be administered each day of the

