## **9.6. Randomization and Blinding of Study Drug**

Participants meeting the eligibility criteria and willing to consent to the study procedures will be randomized on a 1:1:1 basis with block sizes of 10 to receive one of the following treatments:

1. Daily FMT treatment with 5 capsules/day
2. One-time FMT treatment of 30 capsules
3. Daily placebo (5 capsules/day)

Randomization will be carried out by the UW PRC so that the research team and treatment team remains blinded to whether the patient is receiving FMT or placebo.

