### *All subjects:*

All subjects will provide stool samples every three days after the baseline visit until their FMT intervention is complete and weekly for one month following conclusion of FMT treatment. Patients will also be asked to complete a patient diary daily from enrollment through the first month of follow-up. If a subject is discharged during the study period, he/she will be asked to complete the patient diary from home as well as provide stool samples to be mailed back to the lab for processing. A member of the study team will also call or email patients on a weekly basis during the intervention and follow-up period to remind to complete the stool sample

as well as record any adverse events. If a patient is discharged, vital signs, general health status, and medications at discharge will be assessed through the medical record.

At the end of the 1 month follow-up (last week of providing the weekly, post-FMT stool samples), patients will receive a call assessing the following:

- Clinical assessment by study nurse or physician, specifically evaluating adverse events related to the intervention.
- Data collection at visit:
  - Interim medical history with focus on infectious diseases
  - Concomitant medication
  - Significant changes in diet
  - Changes in stool consistency (Bristol Stool Scale) and frequency
  - General health status
  - Adverse events (NIH criteria)

A table of all study events is provided in Appendix II, 17.2 (Study Calendar).

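### The over-14-day dosing rule in section 8.4.2.2 swaps the Group 1 and Group 2 labels, so as written it gives the 30-capsule dose to the daily-FMT arm

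*Combined protocol and SAP*

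**What the plan says.** Section 8.4.2.2 (Retention) sets a special rule for patients whose antibiotic course exceeds 14 days. Its first branch reads "Group 1: Patients will be given the 30 capsule dose of FMT on day 16 or 17", explained there as day 14 plus 48 to 72 hours. Its second branch reads "Groups 2 and 3: At 14 days of antibiotics, we will discontinue the daily FMT treatments", after which those patients enter weekly follow-up.

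The arms are defined differently elsewhere. The Study Summary has "Group 2: 30 capsules taken 48-72 hours following conclusion of antibiotic treatment". Section 7.1 says of Group 1: "This group will receive daily oral FMT capsules". The randomization list in section 9.6 has "Daily FMT treatment with 5 capsules/day" as item 1 and "One-time FMT treatment of 30 capsules" as item 2.

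Section 11.2 (All subjects) ties the stool schedule to the end of intervention: samples are due "every three days after the baseline visit until their FMT intervention is complete and weekly for one month following conclusion of FMT treatment".

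**The concern.** This is an operative dosing instruction for an investigational product, and it attaches the wrong arm to each action. Group 2 has no daily capsules to stop, so the text cannot be read as a deliberate change of regimen.

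Three things are at stake if the label is followed:

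- A daily-FMT patient would receive the other active arm's dose on top of daily dosing.
- Daily FMT and daily placebo, which are meant to run on the same schedule, would end at different times.
- Staff would have no clear instruction on when, under this rule, a Group 2 patient takes the single dose.

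The rule can be reached. Recruitment aims at "anticipated short courses (2 weeks or fewer) of antibiotic treatment", but exclusion criterion 17 bars only courses anticipated to exceed 19 days, and a course can be extended after enrolment.

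**Working it through.** **Step 1. Group labels side by side.**

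| Place | Daily FMT | Single 30-capsule dose | Daily placebo |
|---|---|---|---|
| 2, Study Summary | Group 1 | Group 2 | not numbered |
| 7.1 | Group 1 | Group 2 | Group 3 |
| 9.6 (numbered list, no group label) | item 1 | item 2 | item 3 |
| 11.1, Baseline | Group 1 | not mentioned | Group 3 |
| 11.2 | Group 1 | Group 2 | Group 3 |
| 17.2, calendar key | Groups 1 and 3 (daily dosing) | Group 2 | Groups 1 and 3 (daily dosing) |
| **8.4.2.2, over-14-day rule** | **Groups 2 and 3 (daily capsules stopped)** | **Group 1** | **Groups 2 and 3 (daily capsules stopped)** |

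Only the last row disagrees. The days in the rule are right: 14 + 2 = 16 and 14 + 3 = 17. The 48-72 hour window is the one that belongs to the single-dose arm in sections 2, 7.1 and 11.2. The preceding paragraph of 8.4.2.2 itself ties that window to the one-time group and pairs the daily and placebo groups. So the labels are wrong and the regimens are not. The amendment log's entry on moving the cutoff from 19 to 14 days does not concern which arm gets which regimen.

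**Step 2. Size of the misdirected dose.** The Study Summary gives 22.5 g for 30 capsules, so 22.5 / 30 = 0.75 g per capsule. The added dose is 30 capsules, or 22.5 g.

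**Step 3. Total exposure for a daily-FMT patient, full adherence assumed.** Inclusion criterion 6 allows up to 72 hours of antibiotics before enrolment, so first dosing is taken as antibiotic day 1 or day 4.

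| Scenario | From day 1 | From day 4 |
|---|---|---|
| Ordinary regimen, 14-day course (rule not triggered) | (14 + 7) × 5 = 105 | (11 + 7) × 5 = 90 |
| Rule with labels corrected (stop at day 14) | 14 × 5 = 70 | 11 × 5 = 55 |
| Literal rule, daily capsules assumed to end at day 14 | 70 + 30 = 100 | 55 + 30 = 85 |
| Literal rule, daily capsules assumed to continue for course + 7 days, 16-day course | (16 + 7) × 5 + 30 = 145 | (13 + 7) × 5 + 30 = 130 |
| Same, 19-day course | (19 + 7) × 5 + 30 = 160 | (16 + 7) × 5 + 30 = 145 |

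If daily dosing ends at day 14, the literal total is 5 capsules below the ordinary 14-day regimen. It is above that regimen only if daily dosing continues. In that case the excess over the corrected rule is 145 − 70 = 75 to 160 − 70 = 90 capsules. Of this, 115 − 70 = 45 to 130 − 70 = 60 is ordinary course-plus-7-days dosing, and 30 is the misdirected dose.

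**Step 4. End of intervention.** Under the literal rule, daily placebo ends on day 14 and daily FMT ends no earlier than day 16 or 17, a gap of at least 2-3 days. If daily FMT continued for course + 7 days, it would end on day 23 (16-day course) to day 26 (19-day course), a gap of 9-12 days. With corrected labels the gap is 0. Criterion 17 limits the anticipated course and not the actual one, so 12 days is not a strict maximum.

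**Step 5. Stool sampling.** Section 11.2 moves patients to weekly samples when intervention ends. Sections 7.1, 7.2.1 and 8.4.2.2 keep the 3-day schedule while a patient is in hospital, in every group. The arms would therefore diverge only for outpatients and discharged patients. At 2-3 days, the divergence is about one 3-day sampling interval.

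**The case against.** The strongest reply is that nobody would follow the label. The words about a 30-capsule dose, a 48-72 hour window and daily treatment identify the intended arms. The Pharmaceutical Research Center randomizes, and the research and treatment teams are blinded to FMT versus placebo, so they could not separate Group 1 from Group 3 without the center. A Manual of Procedures also exists and may carry correct instructions, though it is not among these documents. This stands as a reason to expect few errors or none. It does not make the sentence correct, and staff should not have to infer who receives 30 capsules.

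Three stronger readings are tempting, and the documents do not support them:

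- *Overexposure.* A reader might set 100 against 70 capsules and conclude that the total is unplanned. An ordinary 14-day course already gives 105. What is new is the 30-capsule dose after daily dosing. The larger totals require daily capsules to continue, which 8.4.2.2 does not say.
- *No FMT for Group 2.* A reader might infer that single-dose patients receive nothing. The rule moves them to weekly follow-up without mentioning their dose, while sections 7.1 and 11.2 still require it. The text is ambiguous and does not cancel the dose.
- *General damage to primary-outcome sampling.* The 3-day schedule is kept for all hospitalized patients, and no primary analysis time point is shown to be affected.

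**Conclusion.** The point holds: the rule is wrong as written, no section reconciles it, and it should be corrected. The consequence is conditional on a course longer than 14 days and on someone acting on the label. Given both, a daily-FMT patient gets an added 30-capsule (22.5 g) dose in a combination no other section describes. The daily FMT and daily placebo arms finish at least 2-3 days apart, with a matching shift in the start of weekly sampling for non-hospitalized patients only. The timing of the Group 2 dose is unclear. The capsule counts assume full adherence and first dosing between antibiotic days 1 and 4. The documents do not say how many patients would have courses over 14 days, and no estimate is made. Sample size, power and the analysis method are unaffected.

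**What to change.** In section 8.4.2.2, change the label on the 30-capsule instruction to Group 2 (single-dose FMT), and the label on the day-14 stop to Groups 1 (daily FMT) and 3 (daily placebo). In the second sentence, say that daily FMT or placebo capsules are discontinued, since Group 3 takes no FMT. Keeping the regimen name beside each number guards against the same slip recurring. If the Manual of Procedures or pharmacy instructions repeat the rule, they should be checked against the corrected text. The cost is a wording correction to two sentences, with no added patients, visits or procedures.
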